Aim 1B: Secondary (short-term) efficacy outcome: Time to restore and maintain medical stability in hospital is defined as days to reverse the medical instability indicators for hospitalization in adolescents with eating disorders. A six-point index will adjudicate daily medical stability: 1.) 24-hour heart rate (HR) ≥ 45 bpm, 2.) systolic blood pressure (SBP) ≥ 90 mmHg, 3.) temperature $\geq 35.6^\circ$ C, 4.) orthostatic increase in HR ≤ 35 bpm, 5.) orthostatic decrease in systolic BP ≤ 20 mmHg, and 6.) $\geq 75\%$ of mBMI. Each of the six criteria were scored as "1" if met, "0" if unmet and missing (not scored) if not measured. Medical stability was considered restored when all criteria were stable for 24 hours, allowing a maximum of two missing values (i.e. participants were considered stable if meeting 4 of 4, 5 of 5 or 6 of 6 measured criteria). All randomized participants who receive at least one day of treatment, including those who withdraw at any time during the refeeding intervention, will be included in the mITT analysis. Specifically, survival analysis with log rank test will compare time to achieve medical stability by arm while accounting for the correlation within sites; participants who do not meet stability criteria by hospital discharge will be right-censored. In case of any important unbalanced covariate at baseline, Cox proportional hazard ratio model will be used to control for the potential bias due to the confounder. Additionally efficacy outcomes will include the proportion achieving medical stability in each arm, change in %mBMI as compared to baseline, and time to restore HR.

Aim 2. Safety: Primary indicator of safety will be incidence of the following electrolyte abnormalities during hospitalization: 2A) hypophosphatemia (<3 mg/dL), 2B) hypomagnesaemia (≤ 1.7 mg/dL), 2C) hypokalemia (< 3.5 mEq/L). These AEs will be tracked, recorded, reported to the DSMB for monitoring, and to the IRB and NIH as needed, according to the attached DSMP. Incidence of the electrolyte abnormalities and proportion receiving supplementation to correct electrolyte abnormalities will be compared by arm during hospitalization using Fisher's exact test. Additional safety outcomes: the proportion receiving electrolyte supplementation during the hospitalization between groups will be compared with Fisher's exact test; time to electrolyte nadir will be compared with Wilcoxon rank sum test.

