Aim 3. Cost Effectiveness (CE): A decision tree of treatment costs, AEs, health care utilized (including rehospitalizations), and remission will compare the CE between the two study arms. The main CE outcome is incremental cost per additional adolescent remitted. Health care utilization will be costed using national data sources such as acquisition costs for medications, Kids-HCUP for hospitalizations, CPT codes for physician visits and mental health visits, and internet-based costs for lab tests. We will use 2014 US costs and not charges. Indirect costs including missed school and workdays will be assessed and costed using national estimates of wages and salaries of this age group from the Bureau of Labor Statistics, in order to estimate loss of leisure time (school) or salary

time (work).

We will determine the incremental CE ratio (ICER) as:

$$\text{ICER} = \text{CostLCR-CostHCR}/\text{Number RecoveredLCR-Number RecoveredHCR}.$$

Effectiveness will also be indicated by cost of rehospitalizations avoided (ie, rehospitalizations in LCR-HCR). We will determine the net monetary benefit (NB) of each treatment option as: $\text{NB} = \text{Effectiveness} \times \text{Willingness To Pay (WTP)} - \text{Cost}$. A positive difference in NB between treatments indicates CE. We will also calculate an acceptability curve to demonstrate how parameter uncertainty affects the likelihood of selecting the optimal treatment at a given WTP threshold. Cost of treatment will be determined by initial hospitalization and 12 mo follow-up costs (not charges) including AEs and rehospitalizations. The HCUMS follow-up survey will assess indirect costs such as lost school and/or work (wages) using national data sources (see **C.2.c.(2)**).

Effectiveness will be determined per aim 1A; ICER will also use time (incremental cost per additional day of recovery time over 12 mo). Cost efficacy will be assessed with short-term outcomes at end of hospitalization. Per Aim 1B, cost-efficacy will be assessed with other short-term outcomes at the end of treatment (hospitalization period). Cost-efficacy will be defined as hospital cost or charges associated with length of stay; group differences will be compared with Wilcoxon rank sum test.

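### Short-term cost-efficacy (SAP 2.2, Aim 3) is defined as hospital cost by length of stay, with no efficacy term, although the SAP ties it to Aim 1B

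*Combined protocol and SAP*

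**What the plan says.** SAP section 1 states that effectiveness for Aim 3 is defined by Aims 1A and 1B together. In SAP 2.2, under Aim 3, the long-term analysis carries this through for Aim 1A: "The main CE outcome is incremental cost per additional adolescent remitted", with an ICER, a net-benefit formula and an acceptability curve.

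The short-term analysis is introduced with "Per Aim 1B, cost-efficacy will be assessed with other short-term outcomes at the end of treatment (hospitalization period". The next sentence is the only operational definition: "Cost-efficacy will be defined as hospital cost or charges associated with length of stay". The method follows directly: "group differences will be compared with Wilcoxon rank sum test".

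On the cost basis, an earlier paragraph of the same Aim 3 text says "We will use 2014 US costs and not charges", whereas the short-term definition accepts either.

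Under Aim 1B in SAP 2.2, "participants who do not meet stability criteria by hospital discharge will be right-censored", and the analysis set covers treated participants "including those who withdraw at any time during the refeeding intervention". Aim 1B also lists the proportion reaching stability in each arm as a further efficacy outcome.

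**The concern.** A cost-efficacy measure should relate what is spent to what is achieved. Here the text names Aim 1B as the source of the effect, but no Aim 1B quantity (proportion stable, time to stability, change in %mBMI) appears in the definition or the test.

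This matters because length of stay can be short for two opposite reasons: stability came quickly, or the participant left without it. Aim 1B separates the two by censoring the second group. The cost measure does not separate them and treats both as savings. An imbalance between arms in departures before index stability would then move the cost-efficacy result in favour of the arm with more of them, possibly against the Aim 1B result for the same hospital period.

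**Working it through.** **Is there a figure to reproduce?** No. The plan gives no cost, length-of-stay, power or sample-size figure for short-term cost-efficacy. The check is a reading of the text followed by an illustration.

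**Step 1: components of each Aim 3 measure.**

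| Measure | Cost term | Effect term |
|---|---|---|
| 12-month ICER | yes | number recovered |
| Net benefit | yes | effectiveness × WTP |
| Short-term cost-efficacy | cost or charges by length of stay | none |

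**Step 2: can a participant leave without index stability?** Yes, by two routes.
- Withdrawal during refeeding, which Aim 1B provides for.
- Ordinary discharge. Protocol 3.1.e makes heart rate the primary discharge criterion, and its full definition tolerates some blood-pressure and orthostatic deviations in asymptomatic patients. The Aim 1B index has six criteria and no such tolerance.

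The rationale for SAP Amendment 2 (Appendix Table 2) also refers to discharge before stability.

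**Step 3: direction of the effect.** Let s be the share leaving stable, S the stay of those leaving stable and E the stay of those leaving unstable, with S and E the same in both arms and E < S.
- Mean stay = s·S + (1 − s)·E = E + s(S − E). This falls as s falls.
- Days per participant stabilised = mean stay / s = S + E(1 − s)/s. This rises as s falls.

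Under these assumptions the two measures always rank the arms in opposite order.

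**Step 4: numbers.** S and E are assumed. The shares 72% and 92% are borrowed from SAP Table 2.B and used here as shares leaving stable. Take S = 10 and E = 5.
- 72% arm: 0.72 × 10 + 0.28 × 5 = 8.60 days; 8.60 / 0.72 = 11.94 days per participant stabilised.
- 92% arm: 0.92 × 10 + 0.08 × 5 = 9.60 days; 9.60 / 0.92 = 10.43 days per participant stabilised.

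The difference in mean stay is (difference in s) × (S − E). Over S = 8 to 12, E = 3 to 7, and 72% versus 92% or 66% versus 78%, it runs from 0.12 × (8 − 7) = 0.12 to 0.20 × (12 − 3) = 1.8 days, always in favour of the less stable arm.

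**Step 5: the planned rank test.** Simulation with 60 per arm and 2,000 replicates. Time to stability is gamma with mean 10 and SD 4 days, the same in both arms and rounded up to whole days. In one arm a share leaves unstable on days 2 to 5.

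| Share leaving early | Significant Wilcoxon result favouring that arm | Days per participant stabilised in that arm |
|---|---|---|
| 0% | 2.6% | 10.5 |
| 10% | 14.9% | 10.8 |
| 20% | 46.1% | 11.3 |
| 30% | 79.0% | 11.9 |
| 40% | 96.1% | 12.6 |

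**Step 6: how far the reversal depends on equal S.** If the more stable arm also stabilises faster, its stay shortens. In the Step 4 example its mean stay equals 8.60 when 0.92·S + 0.40 = 8.60, so S = 8.20 / 0.92 = 8.91 days. A gain of 10 − 8.91 = 1.09 days in time to stability would therefore cancel the spurious advantage.

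**The case against.** The strongest reply is that the harm is conditional and largely visible elsewhere. It requires more departures before index stability in one arm than in the other. The plan provides for such departures but states no rate or imbalance, and SAP 2.3 anticipates non-differential dropout (said of retention). Where discharge follows stability, length of stay is itself partly an efficacy measure. Stability by arm is reported under Aim 1B for the same period, and rehospitalisations enter the 12-month cost-effectiveness analysis. The wording about assessing cost-efficacy with other short-term outcomes could mean simply presenting cost beside them.

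Most of this stands, and it limits the point to a secondary economic result. It does not supply an effect term: side-by-side reporting is a possible intention, but no joint measure is written.

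Two stronger readings are tempting. A reader might infer that the plan will reward early unstable discharge; the documents do not support this, because nothing in them predicts an imbalance. A reader might also take every participant censored in Aim 1B as a premature departure. That is not supported either, since some discharges permitted by protocol 3.1.e would fail the six-point index.

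**Conclusion.** The definition is incomplete as written: followed exactly, the SAP would report a hospital-cost comparison as cost-efficacy, despite its own references to Aim 1B. That conclusion rests on the text alone. The possible reversal of ranking rests on assumed stays, an assumed imbalance in departures, and (Step 4) equal stays among stable leavers in the two arms. The 0.12 to 1.8 days and the simulated rejection rates show direction and plausibility; they do not estimate this trial's bias. The conflict between cost-or-charges and costs-only is a separate small inconsistency in the same text. The point is minor and bears on neither the primary outcome nor the 12-month ICER.

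**What to change.** 1. Relabel the Wilcoxon length-of-stay comparison as *hospital cost*, and use costs throughout so that it agrees with the costs-only rule in Aim 3.
2. Define short-term cost-efficacy as the HCR minus LCR difference in mean hospital cost, reported jointly with the HCR minus LCR difference in the proportion achieving Aim 1B stability, with bootstrap confidence intervals for both. Fix the horizon in advance: by discharge, or by day 14 to match the 2-week timeframe recorded in Appendix Table 2.
3. If net benefit is wanted, follow the SAP's own formula: (difference in proportion stable × WTP) − (difference in mean cost). The documents give no WTP for a stabilised participant, so show it over a stated range.
4. State that protocol 3.1.e discharges not meeting the six-point index count as not stable under the index, and tabulate them separately from withdrawals.
5. Label the analysis post hoc if short-term data have already been analysed by arm. Appendix Table 2 records approval for that analysis and the breaking of the randomisation code.

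The cost is a wording change and one additional analysis of data already collected. If day 14 is chosen, stability must also be scored at a fixed time as well as analysed as a time to event.

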2.3. Power and Sample-size Considerations

Aim 1. Based on studies of AN remission, **Table 2.A** shows that with $N=60$ per arm we have 80% power on 2-sided 0.05-level test to detect a 20% difference (8% vs. 28%) if data were cross-sectional ($\rho=1$). Our longitudinal data will allow detection of smaller effects, especially if the correlation among outcomes is low ($\rho < 0.8$). We anticipate 85% retention and non-differential dropout by arm. Since **time to medical stability** is also expected to differ by at least 12% (**Table 2.B.**), we will be adequately powered for Aim 1B.

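### The short-term hospital cost comparison in Aim 3 leaves cost or charges open, against the plan's own rule, and its only inference is a rank test that gives no mean cost difference (minor)

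*Combined protocol and SAP*

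**What the plan says.** All of the relevant text is in SAP section 2.2, Aim 3.

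- Costing rule, general: "We will use 2014 US costs and not charges".
- Costing rule, with the index stay named: "Cost of treatment will be determined by initial hospitalization and 12 mo follow-up costs (not charges) including AEs and rehospitalizations".
- Main analysis: "The main CE outcome is incremental cost per additional adolescent remitted". It is supported by an ICER, a net monetary benefit and an uncertainty analysis: "We will also calculate an acceptability curve to demonstrate how parameter uncertainty affects the likelihood of selecting the optimal treatment".
- Short-term item: "Cost efficacy will be assessed with short-term outcomes at end of hospitalization". It is linked to Aim 1B.
- Its definition: "Cost-efficacy will be defined as hospital cost or charges associated with length of stay".
- Its analysis: "group differences will be compared with Wilcoxon rank sum test".

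For this short-term item the SAP gives no rule for choosing between cost and charges, no exception to the costing rule, and no mean difference or confidence interval.

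**The concern.** Two things do not fit together.

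First, the measure. A rule that excludes charges, and that names the initial hospitalization, is followed by a definition that admits charges for that same stay. Two analysts following the SAP could analyse different variables, and nothing in the text makes either of them wrong.

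Second, the test. A statement that one strategy costs less in hospital is a statement about mean cost, because the mean times the number of patients is the money spent. A rank-sum test asks whether a randomly chosen participant in one arm tends to have a higher cost than one in the other. The two questions coincide under added assumptions, such as a pure shift between arms, which the SAP does not state. When costs are skewed and the spread differs between arms, the rank test can reject although mean costs are equal. It can also miss a mean difference produced by a few long stays.

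At stake is the wording of a short-term cost conclusion. The main cost-effectiveness result is not at stake.

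**Working it through.** **1. The measure, by reading.** The second costing statement covers the initial hospitalization and excludes charges. The short-term definition covers the same hospitalization and allows charges. Both are current SAP text, so they conflict without any assumption.

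**2. Whether the choice can matter to the rank test.** If one cost-to-charge ratio applied to everyone, ranks would be identical and so would the p-value. The choice matters when the ratio differs by site. An illustration:

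- Site split 75/25. This follows from the SAP's expected eligible numbers: 120/(120 + 40) = 75%.
- Cost-to-charge ratios of 0.30 and 0.45, and a log-cost shift of 0.2 between arms (assumptions).
- 60 per arm, 3,000 simulated trials.

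Mean charges were about 3.1 times mean costs. The rank-sum test was significant at 0.05 in 70% of trials on cost and 62% on charges, and the two verdicts disagreed in about 14% of trials.

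**3. Rank test against mean cost.** The documents give no mean, SD or target difference for hospital cost, so there is no planned figure to reproduce. The distribution is an assumption: log-normal cost, 55 per arm (60 per arm planned, less a few exclusions), two-sided 0.05.

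A log-normal mean is exp(μ + σ²/2). With σ₁ and μ₁ = 0 in one arm, the means are equal when μ₂ = (σ₁² − σ₂²)/2. The rank test responds to

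P(cost₂ < cost₁) = Φ(−μ₂ / √(σ₁² + σ₂²)).

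For σ = 0.4 and 0.8: μ₂ = (0.16 − 0.64)/2 = −0.24, and P = Φ(0.24/√0.80) = Φ(0.268) = 0.606. This differs from 0.5 although the means are the same.

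| Log SD, arm 1 vs arm 2 | μ₂ for equal means | P(cost₂ < cost₁) | Rank-sum rejects | Welch test of means rejects |
|---|---|---|---|---|
| equal (0.4, 0.6 or 0.8) | 0 | 0.500 | about 5% | about 5% |
| 0.4 vs 0.5 | −0.045 | 0.528 | about 8% | about 5% |
| 0.4 vs 0.6 | −0.100 | 0.555 | about 18% | 5–6% |
| 0.4 vs 0.7 | −0.165 | 0.581 | about 31% | about 6% |
| 0.4 vs 0.8 | −0.240 | 0.606 | about 50% | 6–7% |

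With 4,000 or more simulated trials per row, the Monte Carlo standard error is at most √(0.25/4000) = 0.8 percentage points. At 60 per arm the results are similar (18% at 0.4 vs 0.6; 51% at 0.4 vs 0.8).

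**4. The opposite direction.** Take equal medians with log SD 0.5 vs 0.8. The means are exp(0.125) = 1.13 and exp(0.32) = 1.38, a ratio of exp(0.195) = 1.22. The rank test rejects in about 5% of trials, the same as when nothing differs. The Welch test rejects in about 20%.

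**5. The case that favours the planned test.** Take a proportional shift of 0.3 on the log scale with equal spread. At log SD 0.6, rank-sum power is 71% against 66% for Welch. At log SD 0.8 it is 47% against 39%.

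**The case against.** The strongest case for the plan is that a pre-specified rank test on a skewed in-hospital measure is legitimate. It holds its size when the two distributions are equal, and it is somewhat more powerful than a test of means under a proportional shift. The 50% figure is not a type I error in the test's own terms, because the distributions do differ there. It also needs one arm to have twice the log-scale spread of the other. Nothing in the documents suggests that: both arms share the same hospitals and discharge criteria. All of this stands, and it is why the size is given as a range starting at 5%.

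Three stronger readings are tempting, and the documents do not support them.

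- A reader might infer that the cost-effectiveness conclusion of Aim 3 rests on a rank test. It does not. The ICER, net benefit and acceptability curve use arm-level cost and are specified separately.
- A reader might infer that the short-term result could contradict the ICER and that the fix would prevent this. The ICER covers the index stay, 12 months of follow-up, adverse events and rehospitalizations, relative to remission. The short-term item covers the index stay alone. The two could differ however the short-term item is analysed.
- A reader might infer that the measure was picked after results were seen. The SAP leaves that possible by not fixing the measure. Nothing in it shows that it happened.

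The objection does not answer two points: the conflict over charges, and the absence of any mean difference or interval for the short-term comparison.

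**Conclusion.** The point holds, as a minor one on a secondary analysis.

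The conflict between the costing rule and the short-term definition is a matter of text and needs no assumption. Its numerical effect does: the 14% disagreement rests on assumed site cost-to-charge ratios and an assumed arm difference.

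The rank-sum test is not wrong for the hypothesis it tests. It is incomplete for an economic comparison, because it yields no estimate of mean cost difference. With equal mean costs, log-normal data and 55 per arm, its rejection rate runs from about 5% at equal spread to about 50% at log SD 0.4 vs 0.8. If the arms have similar spread, the practical consequence is small. No primary, safety or 12-month cost-effectiveness result changes.

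**What to change.** 1. Define the short-term measure as hospital cost only, in line with the SAP's own rule, and state its source. If billing data are used, convert charges to cost with a stated site-specific ratio.
2. Make the arm difference in arithmetic mean hospital cost, with a bootstrap confidence interval resampled within arm and site, the main short-term cost comparison. A gamma model with log link and a site term is an alternative; its ratio of means should also be expressed as a cost difference.
3. Keep the rank-sum test as supportive, or apply it to length of stay, and word its result as a comparison of distributions.

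The cost is a few sentences in the SAP, a few lines of code and, if charges are the source, the conversion ratios, which the documents do not give. No extra participants or visits are needed. The downside is that the interval for mean cost may be wide: in the example with means 22% apart, a test of means detected the difference in only about 20% of trials. That imprecision is real, and the rank test's p-value does not show it.

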2.3. Power and Sample-size Considerations

Aim 1. Based on studies of AN remission, **Table 2.A** shows that with $N=60$ per arm we have 80% power on 2-sided 0.05-level test to detect a 20% difference (8% vs. 28%) if data were cross-sectional ($\rho=1$). Our longitudinal data will allow detection of smaller effects, especially if the correlation among outcomes is low ($\rho < 0.8$). We anticipate 85% retention and non-differential dropout by arm. Since **time to medical stability** is also expected to differ by at least 12% (**Table 2.B.**), we will be adequately powered for Aim 1B.

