2.4. Data Management

a. DCC: [name] at UCSF will lead the DCC, which will be autonomous and independent of the clinical sites. It is housed in the UCSF Department of Preventive and Restorative Dental Sciences (PRDS). The department is staffed primarily by statisticians and scientific researchers who conduct data-intensive research, collaborative data collection and analyses from multiple sites. They are equipped with an independent network of sophisticated and reliable computer systems with high-level security for protecting health information. The network is maintained by an in-house computer staff, which manages all aspects of the network, including ongoing maintenance, installation and upgrades of hardware, software and structural components such as cabling and servers. [name] is the lead biostatistician and routinely guides the work of Master-level statisticians, data managers and programmers. **[name]** will continue as faculty biostatistician and DCC leader. She has extensive experience running NIDCR-funded DCCs for clinical trials with more than 8-10 sites nationwide. Thus, UCSF has experience maintaining a distinctly separate but closely coordinated working relationship between clinical sites and data center.

Table 2.A Detectable differences in remission--rates:

ρ^*	LCR	HCR	Mo---3 Diff
1.0	8%	28%	20%
0.8	14%	34%	20%
0.6	16%	34%	18%
0.4	18%	34%	16%
0.2	20%	34%	14%
0.1	22%	34%	12%

Table 2.B. Detectable differences in time to medical stability-rates

ρ^*	LCR	HCR	Difference
1.0	72%	92%	20%
0.8	66%	86%	20%
0.6	66%	84%	18%
0.4	66%	82%	16%
0.2	66%	80%	14%
0.1	66%	78%	12%

*correlation among 5 time points within participant

b. Electronic data capture: Both clinical sites are equipped with the same Research Electronic Data

Capture (Qualtrics) system for databases, data entry forms, online questionnaires and data validation. Data will be automatically exported to STATA or SAS for analysis using The Data Export Utility. The DCC uses advanced features including branching logic for dynamic data entry form generation, file uploading, data importing, and embedded calculated database fields.

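### The SAP calls Aim 1B adequately powered at a 12% difference, but Table 2.B reaches 12% only with repeated-measures credit that the log-rank test does not use

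*Combined protocol and SAP*

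**What the plan says.** SAP section 2.3 sets power for Aim 1 at 60 per arm, two-sided 0.05. For remission (Table 2.A) it claims 80% power "to detect a 20% difference (8% vs. 28%) if data were cross-sectional", which it labels rho = 1. It then explains why smaller differences come into reach: "Our longitudinal data will allow detection of smaller effects, especially if the correlation among outcomes is low". For Aim 1B it says that time to medical stability "is also expected to differ by at least 12"%, cites Table 2.B, and concludes that "we will be adequately powered for Aim 1B".

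Table 2.B (printed in section 2.4) runs from rho = 1.0 (72% vs 92%, 20 points) to rho = 0.1 (66% vs 78%, 12 points). The footnote defines rho as the "correlation among 5 time points within participant".

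SAP section 2.2 gives the Aim 1B analysis: "survival analysis with log rank test will compare time to achieve medical stability by arm", and "participants who do not meet stability criteria by hospital discharge will be right-censored". It also keeps a binary version: "Additionally efficacy outcomes will include the proportion achieving medical stability in each arm". No hazard ratio, expected number of events or censoring proportion is given for the log-rank test.

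**The concern.** The power statement and the analysis describe different data. Table 2.B assumes five measurements per participant and gains precision when they are weakly correlated. The log-rank test takes one event or censoring time from each participant. By the SAP's own reasoning, data without a longitudinal gain correspond to rho = 1, and that row of Table 2.B shows 20 points, not 12. The SAP says this of Table 2.A; Table 2.B has the same rho column and footnote.

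At stake is how an Aim 1B result is read. Someone who trusts the stated power at 12 points could take a non-significant result as stronger evidence of no difference than the design supports. SAP Appendix Table 2 (Amendments 1 and 2) suggests how this arose: Aim 1B moved from a mixed model over follow-up to an in-hospital survival analysis. The point does not depend on that history, because sections 2.2 and 2.3 and Table 2.B are all current text.

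**Working it through.** **Inputs.** 60 per arm and two-sided 0.05 (SAP 2.3, stated for Table 2.A and taken to apply to Table 2.B); the proportions and rho values in Table 2.B; m = 5 time points (table footnote).

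**Step 1: reproduce Table 2.B.** The SAP prints no formula. The usual design effect for the mean of m equally correlated measurements is DE = (1 + (m − 1)·rho)/m = (1 + 4·rho)/5, with effective n = 60/DE. Power for two proportions with pooled variance under the null is

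Φ{ [d·√n − 1.96·√(2·p̄(1 − p̄))] / √(p₁(1 − p₁) + p₂(1 − p₂)) }.

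For rho = 0.1: DE = 1.4/5 = 0.28 and n = 60/0.28 = 214. With d = 0.12 and p̄ = 0.72, the argument is (0.12·√214.3 − 1.96·0.635)/0.629 = 0.81, so power is 79%. All six rows come out at 79% to 82% (table below), so the formula fits and the table's sums are not in dispute.

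**Step 2: one binary outcome per participant.** Same formula with n = 60. For 66% vs 78%: (0.12·√60 − 1.96·0.635)/0.629 = −0.50, so power is 31%.

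**Step 3: log-rank test.** Assume proportional hazards and read the table's percentages as the proportions stable by a common time. Then HR = ln(1 − p_HCR)/ln(1 − p_LCR), events = 60·(p_LCR + p_HCR), and power = Φ(½·√events·ln HR − 1.96) (Schoenfeld). For 66% vs 78%: HR = ln 0.22/ln 0.34 = 1.514/1.079 = 1.40; events = 60 × 1.44 = 86; ½·√86.4·ln 1.4035 = 1.575; power = Φ(−0.385) = 35%.

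| rho | LCR vs HCR | Points | Step 1, with credit | Step 2, two proportions, n = 60 | HR | Events | Step 3, log-rank |
|---|---|---|---|---|---|---|---|
| 1.0 | 72% vs 92% | 20 | 82% | 82% | 1.98 | 98 | 92% |
| 0.8 | 66% vs 86% | 20 | 81% | 73% | 1.82 | 91 | 82% |
| 0.6 | 66% vs 84% | 18 | 79% | 63% | 1.70 | 90 | 71% |
| 0.4 | 66% vs 82% | 16 | 80% | 52% | 1.59 | 89 | 59% |
| 0.2 | 66% vs 80% | 14 | 82% | 41% | 1.49 | 88 | 47% |
| 0.1 | 66% vs 78% | 12 | 79% | 31% | 1.40 | 86 | 35% |

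For 80% power at HR 1.40 the log-rank test needs 4·(1.96 + 0.84)²/(ln 1.4035)² ≈ 274 events. At 72% average stability that is 274/0.72 ≈ 381 participants, about 190 per arm.

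**Step 4: how far the 35% depends on assumptions.** The SAP gives no timing, so two alternatives were tried.

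- *Final proportions held at 66% and 78%, timing varied.* Simulated log-rank power, 60 per arm, 2,000 runs per setting. The 14-day window and beta-shaped event times are assumptions of this review, not of the SAP. Power is 11–13% if HCR responders stabilise 1 day later, 27–29% with equal timing, 47–50% if 1 day earlier, 64–70% if 2 days earlier and 80–86% if 3 days earlier.
- *12% read literally as a 12% shorter time.* With Weibull shape k, HR = (1/0.88)^k. From 86 to 120 events, power is 9–10% for k = 1, 22–29% for k = 2, 43–56% for k = 3 and 66–80% for k = 4.

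**The case against.** The best counter-argument is that low power has not been shown. The 31% and 35% figures need the table's percentages to be final proportions at a common time, and the 35% also needs proportional hazards; the SAP commits to neither. A log-rank test uses timing as well as the final proportion, and Step 4 shows it could reach 80% or more at 12 points if HCR acts about three days faster. This stands, and it limits the conclusion: the claim is unsupported, not proven false.

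It can also be said that the rho = 1.0 row is not the log-rank limit. That is correct. Under proportional hazards that row has 92% log-rank power, and 80% is reached at about 17.5 points from a 72% base or about 20 points from a 66% base. The row shows what the SAP's table offers without repeated-measures credit, no more.

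Daily stability scores might be called repeated measures, but they only fix the day of the event. The test then uses one time per participant, so the variance reduction in Table 2.B does not carry over.

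Finally, Aim 1B is secondary, Protocol section 2 powers the study on Aim 1A, and a null result should be judged by its confidence interval. All true, and it keeps the point modest. But the SAP chose to make an explicit power claim for Aim 1B, and the claim should match the test.

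**Conclusion.** The concern holds. The statement that Aim 1B is adequately powered at 12% rests on five correlated measurements per participant at rho = 0.1, which multiplies the effective sample by 1/0.28, about 3.6. The log-rank analysis has no such measurements, and the SAP offers nothing else in support.

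With the table's percentages as final proportions and proportional hazards, power at 12 points is about 35% rather than about 80%. Under other timing assumptions it ranges from about 9% to 86%, and the documents do not say where in that range the trial was expected to lie. At about 20 points the log-rank test does reach roughly 80% under proportional hazards (82% for 66% vs 86%). The mismatch between the power basis and the test is certain from the text; the size of the shortfall is conditional. Endpoint, test and sample size are not called into question.

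**What to change.** 1. In SAP section 2.3, withdraw the inference that an expected difference of at least 12% makes Aim 1B adequately powered.
2. Remove the Table 2.B rows with rho below 1.
3. The rho = 1.0 row may stay if labelled as a two-proportion calculation (72% vs 92%, 60 per arm, 82% power) for the proportion achieving stability, which section 2.2 retains as an outcome.
4. Add a log-rank statement, for example: *With 60 per arm and a two-sided 0.05 log-rank test, power is [x]% for a hazard ratio of [y], assuming [z] participants reach stability before discharge and the rest are censored.* The values must come from the sponsor's planning assumptions, not from observed results. If no such assumptions were recorded, say so rather than choose values afterwards.

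The cost is some wording and one table, and a less favourable power statement. No patients are added and neither endpoint nor test changes. Appendix Table 2 dates the short-term database lock 07/31/2019, so the correction is documentary; its use is in how the Aim 1B result is reported and read.
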